3.4.3 Anemia

Inclusion criteria for the study will require adequate entry Hgb value. Respective hematological parameters will be monitored every week up to Week 5 and then every 2 weeks thereafter. Risk management measures are provided in Section 6.5.4.4.

3.4.4 Alterations in Wound Healing or Repair of Tissue Damage

Alternations of wound healing and tissue damage repair are considered as an important potential risk given the $TGF\beta$ mechanism. Management should be discussed with the Medical Monitor on a case-by-case basis. In general, a 2 week delay from treatment is recommended following minor surgery and a 4 week delay for major surgery, but cases should be discussed with the Medical Monitor.

1

3.4.5 Rash with Hyperkeratosis/Keratoacanthoma/Squamous Cell Carcinoma of the Skin

Phase I information from a TGF antibody showed excess acanthomas, some with atypical features, and one confirmed squamous cell carcinoma (Morris 2014). A genetic disorder in the TGF pathway is also known to be associated with skin tumors (Goudie 2011). Based on this information, skin tumors are considered a potential risk. Monitoring will include skin assessments as defined in the Schedules of Assessments (see Table 1 and Table 2). Management should be discussed with the Medical Monitor on a case-by-case basis. Dermatological consults should be requested as needed. Rash with hyperkeratosis/keratoacanthoma/squamous cell carcinoma of the skin are considered as an important identified risk and AESIs requiring expedited reporting from the Investigator to the Sponsor. Any suspicious lesion should be biopsied. For nonserious AESIs, an AESI Report Form has to be completed; for serious events, an SAE Report Form has to be used (see Section 7.4.1.4).

3.4.6 Embryofetal Toxicity

Embryofetal toxicities are a known risk of the PD-1/PD-L1 targeting class. Animal models link the PD-1/PD-L1 signaling pathway with maintenance of pregnancy through induction of maternal immune tolerance to fetal tissue. Based on its mechanism of action (MoA), MSB0011359C may cause fetal harm when administered to a pregnant female and conferred as an important potential risk. An appropriate contraception warning is provided in this clinical protocol. Subjects with pregnancy or in lactation period are prohibited from enrolling in clinical trials.

3.4.7 Mild to Moderate Mucosal Bleeding Events

Mucosal bleeding events of mild to moderate severity were observed in participants treated with M7824 in ongoing studies and are a potential risk for M7824. Events may include epistaxis, hemoptysis, gingival bleeding, or hematuria amongst others. In general, these reactions resolve without discontinuation of treatment.

3.4.8 Potential Benefit

A direct benefit is considered unlikely for participants in this Phase I trial, especially in the low doses of the dose escalation part; therefore only subjects with malignancies for which no standard effective therapy exists or subjects having experienced a failure of standard therapy are eligible for this part of the trial. However, preliminary results from the EMR100070-001 trial with the parent avelumb antibody demonstrate promising clinical antitumor activity.

1

In conclusion, the risk-benefit ratio of treatment with MSB0011359C in the targeted trial population appears positive given the poor prognosis of subjects with advanced malignancies with no standard treatment options.

This clinical study will be conducted in compliance with the clinical study protocol, standards stipulated in Article 14, Paragraph 3, and Article 80-2 of the Pharmaceutical Affairs Law; and "Ministerial Ordinance on Standards for the Implementation of Clinical Studies on Pharmaceutical Product (GCP).

4 Trial Objectives

4.1 Primary Objective

The primary objective of the trial is to determine the safety, tolerability and MTD administered as monotherapy of MSB0011359C in subjects with metastatic or locally advanced solid tumors.

4.2 Secondary Objectives

The secondary objectives are:

- To characterize the PK profile of MSB0011359C
- To evaluate the immunogenicity of MSB0011359C and its relationship to drug exposure
- To assess the best overall response (BOR) according to RECIST 1.1 (Eisenhauer 2009).

Global Version ID:

5 Investigational Plan

5.1 Overall Trial Design and Plan

This is a Phase I, open-label, dose escalation trial to investigate the safety, tolerability, PK, biological and clinical activity of MSB0011359C (M7824) in subjects with metastatic or locally advanced solid tumors with expansion cohorts in selected indications (GC, ESCC, BTC and HCC) in Asia (see Figure 1).

5.1.1 Overall Study Design

5.1.1.1 Dose Escalation

The dose escalation part of this trial will investigate the safety and tolerability of MSB0011359C. It is composed of a standard "3+3" dose escalation design for which 3 to 6 subjects will be enrolled at each dose level depending on the occurrence of DLTs (see Section 5.1.3.3), followed by expansion in cohorts of subjects with GC, ESCC, BTC and HCC (see Figure 1). The dose escalation part and the HCC expansion part of the trial will be conducted in Japan only.

Cohorts of 3 to 6 subjects with metastatic or locally advanced solid tumors, for which no standard effective therapy exists or a standard therapy has failed, will receive MSB0011359C at escalating dose levels (3 mg/kg, 10 mg/kg and 20 mg/kg) once every 2 weeks (see Section 5.1.3.2). The dose range and schedule for this trial were developed based on safety considerations as well as on and experience with the parent avelumab antibody. Up to 18 subjects with metastatic or locally advanced solid tumors are planned for the dose escalation part.

At each dose level, subjects will receive MSB0011359C as a 1-hour (-10 minutes/+20 minutes, ie, over 50 to 80 minutes) intravenous infusion once every 2 weeks until PD has been confirmed by a subsequent scan, unacceptable toxicity, or occurrence of any criterion for withdrawal from the trial or the investigation medicinal product (IMP; see Section 5.5).

Subjects who have experienced CR, PR or SD should be treated through the end of 12 months, although additional treatment is possible. If the Investigator believes that a subject may benefit from treatment beyond 12 months, it may be permissible after discussion with the Medical Monitor. For subjects who achieve CR, PR, or SD on MSB0011359C therapy and then subsequently develop disease progression after stopping therapy, but prior to the end of the study, 1 re-initiation course of treatment at the same dose and schedule and treatment duration up to 12 months is allowed at the discretion of the Investigator and agreement of the trial Medical Monitor (see Section 5.1.6).

Assessment of safety parameters will focus on potential acute side effects that include allergic reactions/hypersensitivities during and immediately following infusion, in the worst case

CONFIDENTIAL

60/167

Global Version ID:

Document No. Object No.

anaphylaxis, which could develop as consequence of an immunogenicity response and might be pronounced due to the immunostimulatory properties of MSB0011359C, promoting an immune response against itself.

Evaluation of safety will also include the incidence and severity of potential irAEs, which may manifest after weeks of treatment (Attia 2005; Calabro 2010; Di Giacomo 2010; Kaehler 2010; Phan 2003; Wolchok 2010). Such immune-mediated AEs may include pneumonitis, colitis, hepatitis, hypophysitis, nephritis, and thyroiditis (hypo- or hyperthyroidism). The spectrum of hypothetical irAEs also includes formation of auto-antibodies such as antinuclear antibodies (ANAs).

Other important risks of the compound include anemia, rash with hyperkeratosis, keratoacanthoma, and squamous cell carcinoma of the skin, as well as alterations in wound healing or repair of tissue damage.

All DLTs will be monitored centrally, and the decision to escalate to the next dose level will be determined by the SMC as outlined in Section 2.2.1.

5.1.1.2 Expansion Cohorts

After determination of the MTD in the dose escalation part, an MSB0011359C dose for further investigation will be selected and enrollment in the expansion cohorts of GC, ESCC and BTC will begin (Figure 1).

After completion of DLT evaluation at 3 mg/kg and 10 mg/kg in the dose escalation part, enrollment in the HCC expansion cohort will start at 3 mg/kg and 10 mg/kg, respectively. Three subjects will be enrolled at 3 mg/kg once the 3 mg/kg dose level in the dose escalation part of the trial has been cleared by the SMC. Six subjects will be enrolled at 10 mg/kg once the 10 mg/kg dose level in the dose escalation part of the trial has been cleared by the SMC. The purpose of the HCC cohort is to further assess the safety of MSB0011359C in subjects with HCC.

Subjects in the expansion cohorts will receive MSB0011359C as a 1-hour intravenous infusion once every 2 weeks until PD has been confirmed by a subsequent scan, unacceptable toxicity or occurrence of any criterion for withdrawal from the trial or the IMP (see Section 5.5).

Subjects who have experienced CR, PR or SD should continue treatment through the end of 12 months after confirmation, although additional treatment is possible. If the Investigator believes that a subject may benefit from treatment beyond 12 months, it may be permissible after discussion with the Medical Monitor. In the case of PD, subjects should continue treatment through their next tumor assessment, if they meet the criteria described in Section 5.5.1. If there is further evidence of PD thereafter, trial treatment should be discontinued; however, continued treatment is possible in consultation with the Medical Monitor. For subjects who achieve a CR, PR, or SD on MSB0011359C therapy and then subsequently develop disease progression after stopping therapy, but prior to the end of the study, 1 re-initiation course of treatment at the same

CONFIDENTIAL INFORMATION

M7824 (MSB0011359C) MSB0011359C in Metastatic or Locally Advanced Solid Tumors in Asia MS200647-0008

dose and schedule and treatment duration up to 12 months is allowed at the discretion of the Investigator and agreement of the trial Medical Monitor (see Section 5.1.6).

For subjects in the GC expansion cohort only, symptom severity will be assessed using 3 patient-reported outcomes questionnaires:

- Patient Global Impression of Severity (PGIS)
- Select items from the European Organisation for Research and Treatment of Cancer Quality of Life Questionnaire Core instrument (EORTC QLQ-C30)
- Select items from the EORTC QLQ-STO22 (stomach cancer module)

For subjects in the ESCC cohort only, symptom severity will be assessed using 3 patient-reported outcomes questionnaires:

[figure not shown]
- PGIS
- Select items from the EORTC QLQ-C30
- Select items from the EORTC QLQ-OES18 (esophageal cancer module)

For subjects in the BTC cohort only, symptom severity will be assessed using 4 patient-reported outcomes questionnaires:

- PGIS
- Select items from the EORTC QLQ-C30
- Select items from the EORTC QLQ-BIL21 (cholangiocarcinoma and gallbladder cancer module)
- Select items from the EORTC QLQ-HCC18 (hepatocellular carcinoma module)

N/N

[figure not shown]
Figure 1 Schematic of Study Design

BTC=biliary tract cancer; ESCC=esophageal squamous cell cancer; GC=gastric cancer; HCC=hepatocellular carcinoma.

Document No. CCl
Object No. CCl

Figure 2 Dose Escalation Schematic

DLT=dose-limiting toxicity; max=maximum; MTD=maximum tolerated dose

5.1.2 Trial Medication Administration and Schedule

will infusion of MSB0011359C Subjects receive intravenous over (-10 minutes/+20 minutes, ie, over 50 to 80 minutes) once every 2 weeks. In order to mitigate potential infusion-related reactions, premedication with an antihistamine and with paracetamol (acetaminophen) (eg, 25 to 50 mg diphenhydramine and 500 to 650 mg paracetamol [acetaminophen] intravenous or oral equivalent) approximately 30 to 60 minutes prior to each dose of MSB0011359C is mandatory for the first 2 infusions. Premedication is optional and at the discretion of the Investigator after the second infusion. If Grade 2 infusion reactions are seen during the first two infusions, then premedication should not be stopped. Steroids as premedication are not permitted.

The trial treatment schedules are provided in the Schedules of Assessments (see Table 1 and Table 2).

The formulation and packaging information of MSB0011359C is provided in Section 6.1 and Section 6.6.

5.1.3 MSB0011359C Dose Escalation

The dose escalation part of the study is expected to enroll up to 18 subjects. Eligible subjects will be patients with metastatic or locally advanced solid tumors who have failed standard therapies or who have no standard effective therapy available.

CONFIDENTIAL INFORMATION

5.1.3.1 Starting Dose

The starting dose of MSB0011359C will be 3 mg/kg.

5.1.3.2 Dose Escalation

The dose escalation will use a standard 3+3 scheme with the following planned doses:

- 3 mg/kg
- 10 mg/kg
- 20 mg/kg

The DLT period is defined as 21 days after the start of therapy. The first subject of each cohort will be observed for at least 5 days before the second subject can be treated. Thereafter, within each cohort, 48 hours must pass before a new subject can initiate dosing. Once the 3 or 6 subjects have passed the 21-day DLT evaluation period, the SMC will review the safety and available PK data to decide upon further dose escalation. Pharmacokinetics data from the previous cohort will be required for SMC review (eg, when the SMC is reviewing safety data from the 10 mg/kg cohort, available PK data from the 3 mg/kg cohort); however, PK data from the cohort under review will not be required).

For each dose level, DLTs are assessed during the first 3 weeks (Figure 1). The criteria for moving from one dose level to another do not allow escalation to the next cohort in cases where more than 1 subject in a cohort experience a DLT. If 1 of 3 subjects in a cohort experiences a DLT, this cohort will be expanded to 6 subjects with the SMC meeting after the 6th subject completes the DLT evaluation period.

The MTD is defined as the highest dose where no more than 1 subject out of 6 subjects experiences a DLT. Thus, the MTD cohort should accrue a total of 6 subjects (Figure 2).

After completion of the DLT evaluation at 3 and 10 mg/kg in the dose escalation part, enrollment in the HCC expansion cohort will start at 3 and 10 mg/kg, respectively.

After determination of the MTD in the dose escalation part, an MSB0011359C dose for further investigation will be selected and enrollment in the expansion cohorts of subjects with GC, ESCC, and BTC will begin (Figure 1).

The DLT criteria will not apply to any of the expansion cohorts.

5.1.3.3 Dose-Limiting Toxicity

A DLT is defined as any Grade \geq 3 AE, with the exceptions described hereafter, assessed as related to IMP by the Investigator and/or Sponsor (ie, Grade \geq 3 adverse drug reaction [ADR]; grading

CONFIDENTIAL INFORMATION

according to the National Cancer Institute (NCI) Common Terminology Criteria for Adverse Events Version 4.03 [CTCAE v4.03]) occurring in the DLT evaluation period (21 days after first administration of MSB0011359C) confirmed by the SMC to be relevant for the IMP treatment. The SMC recognizes that in the absence of prior human experience with MSB0011359C, a conservative approach will be adopted in ascribing the relevance of the treatment-related toxicity to IMP. Treatment-related SAEs will be ascribed as related to drug except where a clear relationship to the underlying disease or recognized comorbidities is evident.

A DLT is defined as the following:

Any Grade \geq 3 AE that is related to MSB0011359C, occurring during the DLT evaluation period (21 days after administration of MSB0011359C), **except** for those listed below. Also, elevated alanine aminotransferase (ALT) or aspartate aminotransferase (AST) 3 times the upper limit of normal (ULN) and a concomitant elevation of bilirubin 2 times the ULN attributable to study drug constitutes a DLT.

- Grade 3 infusion-related reactions resolving within 6 hours from the end of infusion and controlled with medical management.
- Transient (≤ 6 hours) Grade 3 flu-like symptoms or fever, which is controlled with medical management.
- Transient (≤ 24 hours) Grade 3 fatigue, local reactions, headache, nausea, emesis that resolves to Grade < 1.
- Any Grade ≥ 3 drug-related amylase or lipase abnormality that is not associated with symptoms or clinical manifestations of pancreatitis.
- Grade 3 Hgb decrease (< 8.0 g/dL) that resolves to at least 9 g/dL within 14 days or the changes in the associated RBC parameters resolve within 14 days without blood transfusion or erythroid growth factor use.
- Malignant skin lesion that is local and can be resected with negative resection margin.

Dose-limiting toxicities that require treatment discontinuation are described in Section 5.1.7.2.

Subjects who do not complete the DLT observation period for reasons other than a DLT will be replaced.

5.1.4 Expansion Cohorts

After completion of DLT evaluation at 3 and 10 mg/kg in the dose escalation part, enrollment in the HCC expansion cohort will start at 3 and 10 mg/kg, respectively.

After confirmation of tolerability at 20 mg/kg in the dose escalation part, the MSB0011359C dose for further investigation is 1200 mg in the expansion cohorts of subjects with GC, ESCC, and BTC after confirmation by the SMC.

CONFIDENTIAL INFORMATION

5.1.5 Planned Number of Subjects

The planned number of the evaluable subjects for this trial is derived from the dose escalation "3+3" design and the expansion cohort sizes:

The final sample size, however, may vary depending on the total number of dose levels to be escalated and tested, and the subject replacement for DLT evaluations if applicable.

In the event that rapid recruitment in the expansion phase impacts supply of IMP, the screening of new subjects for any cohort may be temporarily paused with 24 hours' notice to investigators.

5.1.6 Planned Treatment Duration

The trial duration for a subject is estimated to be up to 2 years. This includes:

- Up to 28-day Screening period (decision will be made in this period for subjects' trial inclusion if all eligibility criteria are met).
- 21-day DLT evaluation period.
- 12-month treatment duration period until confirmed PD, unacceptable toxicity, or any criterion for withdrawal from the trial or IMP occurs (see Section 5.5).
- End-of-Treatment visit 28 days (± 5 days) after the last dose of MSB0011359C administration.
- Safety follow-up period 10 weeks (± 2 weeks) after the last administration of MSB0011359C.
- Long-term follow-up period: Subjects without PD at the End-of-Treatment visit will be followed up for disease progression (computed tomography [CT]/magnetic resonance imaging [MRI] scans every 12 weeks) until PD.
- Planned first subject in (dose escalation): First Quarter (Q1) 2016. Planned date last subject out (dose escalation): Q4 2020. Planned date last subject out (after expansion and follow-up): Q4 2020.

Subjects who have experienced a CR, PR or SD should continue treatment through the end of 12 months after confirmation, although additional treatment is possible. If the Investigator believes that a subject may benefit from treatment beyond 12 months, it may be permissible after discussion with the Medical Monitor. In the case of PD, subjects should continue treatment through their next tumor assessment, if they meet the criteria described in Section 5.5.1.

CONFIDENTIAL INFORMATION

For subjects who achieve a CR, PR, or SD on MSB0011359C therapy and then subsequently develop disease progression after stopping therapy, but prior to the end of the trial, 1 re-initiation course of treatment at the same dose and schedule and treatment duration up to 12 months is allowed at the discretion of the Investigator and agreement of the trial Medical Monitor. In order to be eligible for retreatment, the subject must not have experienced any toxicity that led to treatment discontinuation of the initial MSB0011359C therapy. Prior to re-initiation of the trial treatment, malignant disease needs to be radiologically re-staged to assess all known sites of the disease and to establish a new baseline for subsequent tumor measurements. Relevant safety laboratory results must be available and verified prior to re-initiating of treatment. Subjects who re-initiate treatment will stay on trial and will be treated and monitored according to the Schedule of Assessments for the expansion part of the trial starting at Week 1, Day 1 (see Table 2).

Moreover, any ADRs should be followed until they resolve, return to Baseline, or stabilization or are irreversible, or when the subject starts a new anticancer therapy (see Section 7.1.5 for details).

5.1.7 Dose Modification and Adverse Drug Reactions Requiring Treatment Discontinuation

5.1.7.1 Dose Modification

The dose of MSB0011359C will be calculated based on the weight of the subject determined on the day prior to or the day of each drug administration.

Each subject will stay on the MSB0011359C dose level assigned in the trial unless treatment needs to be stopped. Dosing modifications (changes in infusion rate) and dose delays are described in Section 5.1.7.2 and Section 6.5.4 and subsections. There are no dose reductions.

5.1.7.2 Adverse Drug Reactions Requiring Treatment Discontinuation

Certain ADRs, defined in this trial as any AE assessed as related to MSB0011359C by the Investigator and/or Sponsor, may require permanent treatment discontinuation of MSB0011359C (listed below). For certain ADRs assessed to be immune-related, Table 5 criteria may supersede this section. These criteria may allow the subject to continue on study if medically indicated after consultation with Medical Monitor.

Any Grade 4 ADRs require permanent treatment discontinuation except for single laboratory values out of normal range that do not have any clinical correlate, and resolve to Grade ≤ 1 within 7 days with adequate medical management.

Any Grade 3 ADRs require treatment discontinuation except for any of the following:

• Transient (≤ 6 hours) Grade 3 flu-like symptoms or fever, which is controlled with medical management.

CONFIDENTIAL INFORMATION

- Transient (≤ 24 hours) Grade 3 fatigue, local reactions, headache, nausea, emesis that resolves to ≤ Grade 1.
- Tumor flare phenomenon defined as local pain, irritation, or rash localized at sites of known or suspected tumor.
- Any Grade ≥ 3 drug-related amylase or lipase abnormality that is not associated with symptoms or clinical manifestations of pancreatitis. The trial Medical Monitor should be consulted for such Grade ≥ 3 amylase or lipase abnormalities. If the amylase or lipase abnormality not associated with symptoms or clinical manifestations of pancreatitis has not resolved to Grade ≤ 1 within the subsequent 2 cycles (28 days), the subject should permanently discontinue treatment with MSB0011359C.
- Grade 3 Hgb decrease (< 8.0 g/dL) that is clinically manageable with blood transfusions or erythroid growth factor use does not require treatment discontinuation. During the 21-Day DLT period, a Grade 3 Hgb decrease (< 8.0 g/dL) will require treatment discontinuation, unless it resolves to at least 9 g/dL within 14 days or the changes in the associated RBC parameters resolve within 14 days without blood transfusion or erythroid growth factor use.
- Increases in Eastern Cooperative Oncology Group performance status (ECOG PS) ≥ 3 that resolves to ≤ 2 by cycle Day 1 of the next cycle (infusions should not be given if the ECOG PS is ≥ 3 on the day of IMP administration and should be delayed until ECOG PS ≤ 2).
- Keratoacanthoma and squamous cell carcinoma of the skin. Any suspicious skin lesion should be biopsied and be surgically removed. The Study Medical Monitor should be consulted.
- Grade 3 or 4 dematological irAEs, treatment should be delayed and treatment started according to Table 5, if condition improves to Grade 1, treatment may be resumed. If ≥ 2 consecutive doses are missed, the Medical Monitor should be consulted.
- Grade 3 or 4 symptomatic endocrinopathies (eg, thyroiditis or hypophysitis), treatment should be delayed and treatment started according to Table 5, if condition improves to Grade 1, treatment may be resumed. If ≥ 2 consecutive doses are missed, the Medical Monitor should be consulted
- Other immune-related ADRs, see Table 5.

Any Grade 2 ADR should be managed as follows:

- If a Grade 2 ADR resolves to Grade ≤ 1 by the last day of the current cycle, treatment may continue.
- If a Grade 2 ADR does not resolve to Grade ≤ 1 by the last day of the current cycle but is manageable and/or not clinically relevant, the ADR should be discussed with the medical monitor. Based on the discussion, it is possible that the infusion will be given on the following cycle. If at the end of the following cycle, the event has not resolved to Grade 1,

CONFIDENTIAL INFORMATION

another discussion should occur with Medical Monitor to consider permanently discontinuing treatment with MSB0011359C.

- Upon the second occurrence of the same Grade 2 ADR in the same subject (except for fatigue and hormone insufficiencies that can be managed by replacement therapy), continuation of treatment with MSB0011359C has to be discussed with the medical monitor and may lead to permanently discontinuation.
- Infusion-related reactions and hypersensitivity reactions (Grades 1 to 4) should be handled according to the guidelines provided in Section 6.5.4.1 and Section 6.5.4.2, respectively.
- Anemia should be handled according to the guidelines provided in Section 6.5.4.4.
- If immune-related ADRs, see Table 5.

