7.1.2 Treatment Period

For this protocol, a cycle is defined as 14 days. In this trial, the treatment will be given until confirmed progression, unacceptable toxicity, or any criterion for withdrawal from the trial or IMP occurs (see Section 5.5). Subjects who have experienced a CR, PR or SD should continue treatment through the end of 12 months after confirmation, although additional treatment is possible. If the Investigator believes that a subject may benefit from treatment beyond 12 months, it may be permissible after discussion with the Medical Monitor. In the case of PD, subjects should continue treatment through their next tumor assessment, if they meet the criteria described in Section 5.5.1.

1

For subjects who achieve CR, PR, or SD on MSB0011359C therapy and then subsequently develop disease progression after stopping therapy, but prior to the end of the trial, 1 re-initiation course of treatment at the same dose and schedule and treatment duration up to 12 months is allowed at the discretion of the Investigator and agreement of the trial Medical Monitor. In order to be eligible for retreatment, the subject must not have experienced any toxicity that led to treatment discontinuation of the initial MSB0011359C therapy. Prior to re-initiation of the trial treatment, malignant disease needs to be radiologically re-staged to assess all known sites of the disease and to establish a new baseline for subsequent tumor measurements. Relevant safety laboratory samples must be drawn and results available and verified prior to re-initiating of treatment. Subjects who re-initiate treatment will stay on trial and will be treated and monitored according to the Schedule of Assessments for the expansion part of the trial (see Table 2).

Subjects will be asked to visit the investigational site according to the Schedules of Assessments (see Table 1 and Table 2). A time window of up to 3 days before or 1 day after the scheduled visit day (-3/+1 days) will be permitted for all trial procedures (except on Day 2 and the Day 43 to 50 visit). In addition, the tumor evaluation (see Section 7.3) has a tumor assessment visiting time window of 5 days prior to dosing (-5 days). Furthermore, if any Screening procedures are conducted within 3 days prior to Day 1 of trial treatment (Week 1, Day 1), the assessments scheduled on Week 1, Day 1 do not need to be repeated except for the evaluation of AEs and concomitant medications.

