Non-permitted concomitant medication during the study	Concomita nt Medication	Blood transfusions and erythroid growth factors were administered to a patient during the 21 days DLT window during the dose escalation phase.	PDEV44	6.5.2	Medical Review	
Withdrawal from treatm	nent/trial					
Subjects that developed withdrawal criteria whilst on study but were not withdrawn;	Other Criteria	Subject became pregnant, but continued on study.	PDEV45	5.5.1	Medical Review Required. Programmed	
Subjects that developed withdrawal criteria whilst on study but were not withdrawn;	Other Criteria	Subject developed any Grade ≥ 3 ADRs or repetitive Grade 2 ADRs, but continued on study.	PDEV46	5.5.1	Medical Review	
Subjects that developed withdrawal criteria while on the study but were not withdrawn;	Other Criteria	Subjects were not withdrawn despite therapeutic failure requiring urgent additional drug.	PDEV47	5.5.1	Medical Review	
Other Criteria						
Subjects dosing error (≥ +/- 20% assigned dose)	IP Complianc e	Subject had dosing error.	PDEV48	6.2	Programmed	
* Programmed by Data M	Other Criteria	Other protocol deviation	PDEV99	Medical defined	Medical Review	

^{*} Programmed by Data Management team.

Signature Page for VV-CLIN-253237 $\,\mathrm{v}4.0$

Approval	PPD
	-2022 23:39:57 GMT+0000

Signature Page for VV-CLIN-253237 v4.0

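### Protocol Section 5.1.7.2 gives opposite instructions for an asymptomatic Grade 4 amylase or lipase abnormality that resolves between day 8 and day 28

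*Protocol*

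**What the plan says.** Protocol Section 5.1.7.2 sets separate discontinuation rules for Grade 4, Grade 3 and Grade 2 adverse drug reactions.

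- **Grade 4 rule.** "Any Grade 4 ADRs require permanent treatment discontinuation except for single laboratory values out of normal range that do not have any clinical correlate". The exempted values must also "resolve to Grade ≤ 1 within 7 days with adequate medical management". No other exception is attached to this sentence.
- **Grade 3 rule.** Grade 3 reactions require discontinuation, subject to a list of exceptions. One bullet in that list covers "Any Grade ≥ 3 drug-related amylase or lipase abnormality that is not associated with symptoms or clinical manifestations of pancreatitis". It asks for consultation with the Medical Monitor and sets its own limit: if such an abnormality "has not resolved to Grade ≤ 1 within the subsequent 2 cycles (28 days), the subject should permanently discontinue treatment with MSB0011359C".
- **Skin and endocrine bullets.** The same list names Grade 3 or 4 dermatological immune-related events and Grade 3 or 4 symptomatic endocrinopathies. Dosing is delayed, and "if condition improves to Grade 1, treatment may be resumed".
- **Opening of the section.** For certain immune-related reactions, Table 5 is allowed to take precedence over the section, and continuation is tied to consultation with the Medical Monitor.

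Section 5.5.1 makes Grade 3 or higher reactions a withdrawal criterion as Section 5.1.7.2 defines them.

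**The concern.** The amylase/lipase bullet is placed as an exception to the Grade 3 rule, yet its scope runs upward from Grade 3 and so includes Grade 4. The Grade 4 rule has only one exception, with a shorter limit. An investigator with an asymptomatic Grade 4 lipase value can therefore find two answers on the same page.

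The section governs stopping for toxicity at every dose level and in every cohort. If sites follow different sentences, subjects with the same event are treated differently. The counts of events leading to permanent discontinuation, which SAP Section 16.1.2 tabulates, would then partly reflect which sentence was read. Those counts help describe tolerability, which is part of the primary objective.

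**Working it through.** There is no sample-size or error-rate figure to reproduce. The check is a comparison of texts with a small amount of arithmetic.

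**Inputs**
- Limit in the Grade 4 exception: 7 days (Section 5.1.7.2).
- Limit in the amylase/lipase bullet: 2 cycles, stated as 28 days (Section 5.1.7.2).
- Cycle length: "For this protocol, a cycle is defined as 14 days" (Section 7.1.2).

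**Arithmetic**
- 2 cycles × 14 days = 28 days, so the bullet agrees with itself.
- Conflicting interval: day 8 to day 28, that is 28 − 7 = 21 days.
- Ratio of the two limits: 28 / 7 = 4.

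**Drug-related Grade 4 amylase or lipase value without pancreatitis**

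| Returns to Grade 1 or below | Grade 4 sentence | Amylase/lipase bullet |
|---|---|---|
| by day 7 | may continue | may continue |
| day 8 to day 28 | permanent discontinuation | may continue |
| not by day 28 | permanent discontinuation | permanent discontinuation |

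The texts differ only in the middle row, and there they are opposed.

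**Does anything else settle it?**
- No sentence in Section 5.1.7.2 ranks the Grade 4 rule against the bullets under the Grade 3 rule.
- The opening clause covers immune-related reactions handled by Table 5. The visible rows of Table 5 are gastrointestinal, dermatological, pulmonary, hepatic, cardiac and endocrine. None addresses amylase or lipase.
- The Grade 3 or higher scope does not look like a slip. The list of exceptions to dose-limiting toxicity in Section 5.1.3.3 uses the same scope for the same abnormality.

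**Skin and endocrine bullets against Table 5**
- *Precedence.* The opening clause permits Table 5 to override but does not say that it does. The endocrine bullet is not worded as limited to immune-related events.
- *Medical Monitor.* The opening clause ties continuation to consultation. The bullets ask for it only when two or more consecutive doses are missed.
- *Resumption after skin events.* Table 5 says to delay or discontinue for Grade 3 to 4, then foresees resumption except in Toxic Epidermal Necrolysis and Stevens-Johnson Syndrome. The bullet says only to delay and names no exclusion.
- *Resumption after endocrine events.* The bullet asks for improvement to Grade 1. Table 5 asks for improvement without naming a grade.

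**The case against.** The best defence is that a specific rule overrides a general one: the amylase/lipase bullet is the more specific, so it governs at Grade 4 too. That is a plausible reading, but the protocol does not state it, and the bullet is attached to the Grade 3 rule only. The bullet also requires Medical Monitor consultation for every such abnormality, which should reduce variation between sites. This stands as mitigation, although the Medical Monitor would be working from the same two sentences. Such events may also be few: Section 7.4.1.1 keeps isolated laboratory findings out of adverse event reporting unless they are symptomatic, lead to discontinuation or are judged medically important.

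Three stronger readings are tempting, and the documents do not support them.

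- *Grade 4 skin and endocrine events get flatly opposite instructions.* The opening clause allows Table 5 to supersede for immune-related events. Table 5 foresees resumption after Grade 3 to 4 rash, with the two named exclusions, and after symptomatic endocrinopathy. Its direction agrees with the bullets. What is left is the misalignment set out in the working.
- *The SAP counts permitted continuation as an important deviation.* Row PDEV46 of SAP Appendix 1 reads "Subject developed any Grade ≥ 3 ADRs or repetitive Grade 2 ADRs, but continued on study", without the exceptions. But the same row is framed as withdrawal criteria that were met without withdrawal. It cites Section 5.5.1, which defers to Section 5.1.7.2, and it is assigned to medical review. No miscoding follows from it.
- *The conflict disturbs the evaluation of dose-limiting toxicity.* Asymptomatic amylase or lipase elevation is exempt from that definition, so a subject stopped before the Day 15 dose would be a non-completer to be replaced. For the 7-day limit to run out by then, the value must be found by about Day 8 (15 − 7 = 8). Amylase and lipase are not core chemistries in Table 8. Table 1 schedules full chemistry only at Screening and Day 15 up to the end of the 21-day window. The case needs an unscheduled finding.

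**Conclusion.** Section 5.1.7.2 contradicts itself for one defined event: an asymptomatic, drug-related Grade 4 amylase or lipase abnormality that returns to Grade 1 or below between day 8 and day 28. This is an internal inconsistency in a stopping rule, not a missing detail. The non-alignment of the skin and endocrine bullets with Table 5 is secondary.

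The day 8 to 28 interval assumes that both clocks start when the Grade 4 value is found. If the two cycles were instead counted from the start of the next cycle, the upper end would move out by at most one cycle, to 28 + 14 = 42 days, and the conflict would widen. It also assumes that the abnormality counts as a single laboratory value under the Grade 4 exception.

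The effect on results is limited and has not been quantified. The primary endpoints in Section 8.3.1 are dose-limiting toxicities and the number, severity and duration of adverse events, not discontinuation rates. The current SAP version postdates the study report and its addendum and cancels the final analysis. The point now matters mainly for reading discontinuations and deviations, and for any reuse of this text.

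**What to change.** The sponsor should reconcile the Grade 4 sentence, the amylase/lipase, skin and endocrine bullets, and Table 5. Each Grade 4 event should carry one instruction, and the text should say which passage takes precedence. The Medical Monitor condition and the conditions for resumption should read the same in both places. Which rule applies is for the sponsor and the Safety Monitoring Committee; this review proposes none.

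As optional tidying, the PDEV46 description in SAP Appendix 1 can refer to reactions as defined in Section 5.1.7.2, to match Section 5.5.1.

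The cost is wording in one protocol section, a check of Table 5 and, if wanted, one SAP row. No procedures, visits or data items are added.
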